4.1 Interim Analysis

No interim analysis is planned for this study.

4.3 Subject Disposition

All subjects will be included in the summary of subject disposition. This will present the overall number of subjects screened by treatment group and overall, the frequency and percentage of subjects randomized and treated, and who completed or discontinued from the study, along with reason for discontinuation.

Furthermore, the number and percentage of subjects in each analysis set will be tabulated. Discontinued subjects will be listed. Subject assignment to analysis sets will be listed. Screen Failures will not be listed or included in summary tables.

4.4 Demographic Characteristics

Individual subject demographics (including age, sex, race and ethnicity) and body measurement data (height, body weight and body mass index) at screening will be listed and summarized by each treatment group and overall for the safety set. If the number of subjects in other analysis sets is different from the safety set by more than 5%, separate demographic tables will be produced.

Height will be measured in centimeters and weight in kilograms. Body mass index will be given in kg/m².

4.6 Inclusion and Exclusion Criteria

The inclusion and exclusion criteria will be listed together with the overall eligibility for each subject.

4.7 Protocol Deviations

The final review of protocol deviations will be performed at the BDRM prior to database lock. The protocol deviations will be listed.

4.8 Medical History

Medical history data will be coded using the Medical Dictionary for Regulatory Activities (MedDRA) dictionary Version 21.0 (or higher) and listed individually. Surgical history data will be listed separately.

4.9 Study Drug Administration

Study drug administration data will be listed individually.

4.10 Prior and Concomitant Medications

All prior and concomitant medications will be coded using the World Health Organization Drug Dictionary version June 2018 or higher and will be listed individually. The frequency and percentage of prior and concomitant medications will be summarized by Anatomical Therapeutic Chemical and Preferred Name. Separate tables will be given for prior and concomitant medications. Prior medications are defined as those for which the end date and time is prior to the date, and time of first study drug administration. Concomitant medications are defined as those with start date and time on or after the date and time of first study drug administration and those with start date and time prior to the first study drug administration but with end date and time on or after the date and time of first study drug administration.

Prior and concomitant medications with missing start (end) date or time will be classified as concomitant medication.

5. Safety Analysis

Safety analyses will be performed on the safety set. Safety parameters will be summarized by treatment groups and, when relevant, overall.

Safety analyses will include an analysis of all AEs, ECGs, clinical laboratory data, vital sign measurements and physical examination results and will be presented using descriptive statistics.

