3.3.4 Precautions to be applied for dosing between subjects within a cohort

A mandatory sentinel dosing strategy of dosing 12 subjects will be used to provide safety assessment in 4 subjects exposed to ATV-PG + AQ. The sentinel group will consist of 4 subjects from treatment 1, and a minimum of 2 subjects each from treatments 2, 3 and 4. Blinded safety data up to 29 days post last dose will be reviewed by a safety review committee (SRC) prior to dosing the remaining subjects.

If the sentinel group shows acceptable safety and tolerability, then the remaining subjects from all four Cohorts will be dosed.

The ratio of allocation to treatment group of the sentinel group has been chosen to ensure the safety of giving ATV+PG and AQ together, in a small number of subjects, while maintaining blinding.

The SRC will make a judgement (based on the minimum data requirements ([Table 4](#)) whether the drug administration to the remaining subjects can continue. See section [4.4](#) for Adverse Reaction (AR) rules.

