3.3.7 Maximum Cohort Size

Following the reporting of an SAE in Cohort 1, it has been agreed between the SRC member to set the maximum cohort size at eight for all subsequent cohorts, with a minimum of one subject from each of the continuing treatment arms. A maximum of three subjects can be on the AQ + Malarone treatment arm within each cohort. This is to improve subject safety. Fewer subjects will ensure that all subjects can be assessed and managed (if required) properly, and everything can be documented properly.

Following the completion of dosing of the first 20 randomised subjects, Treatment 1 has been discontinued from further dosing in accordance with the Adverse Reaction (AR) rules in Section 4.4. Up to 24 further subjects will be included in the study, split in three cohorts of up to eight subjects.

The remaining three treatments will be re-randomised in such a way that across the whole study there will be still 12 subjects dosed with Treatment 2, 12 subjects with Treatment 3 and 12 Subjects with treatment 4. This is taking into account both the already dosed subjects with their originally randomised treatments and the newly randomised subjects yet to be included. Furthermore, within each cohort of up to eight subjects, each of the three treatments (2, 3, and

4) needs to be represented with a maximum of four and a minimum of one subject in the same cohort.

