3.1 Overall Design

Fifty-two subjects will be enrolled and randomized to one of the four treatment (Cohorts 1 to 4) in a ratio of 4:3:3:3 as described below:

- Treatment 1 (n=16) - ATV-PG 1000-400 mg + AQ 612 mg;
- Treatment 2 (n=12) - ATV-PG 1000-400 mg + AQ unmatched placebo;
- Treatment 3 (n=12) - ATV-PG unmatched placebo + AQ 612 mg;
- Treatment 4 (n=12) - ATV-PG unmatched placebo + AQ unmatched placebo.

Following the completion of dosing of the first 20 randomised subjects, Treatment 1 has been discontinued from further dosing in accordance with the Adverse Reaction rules of the protocol. Up to 24 further subjects will be included in the study, split in three cohorts of up to eight subjects.

The remaining three treatments will be re-randomised in such a way that across the whole study there will be still 12 subjects dosed with Treatment 2, 12 subjects with Treatment 3 and 12 Subjects with treatment 4. This is taking into account both the already dosed subjects with their originally randomised treatments and the newly randomised subjects yet to be included. Furthermore, within each cohort of up to eight subjects, each of the three treatments (2, 3, and 4) needs to be represented with a maximum of four and a minimum of one subject in the same cohort.

Due to randomization scheme with the initial 20 subjects, a total of 8 subjects have received treatment 1 before it was decided to terminate this arm.

Subjects will be screened within 20 days prior to entering the study on Day -1. Each subject will receive verbal and written information followed by signing of the Informed Consent Form (ICF) prior to any screening procedures taking place. Subjects will be admitted to the study unit on Day -1 and will be discharged on Day 4.

All subjects will attend the unit for an outpatient visit on Days 8, 15, 22, 29 and a follow-up visit on Day 36 +/- 1 day (Figure 1). All the assessments performed during the study are detailed in the study schedule of assessments. Study design features as well as number of subjects may be adapted according to the Adaptive Features. This study will use a sentinel dosing strategy.

[figure not shown]

Figure 1. Study flow chart.

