5.1 Adverse Events

A Treatment Emergent Adverse Event (TEAE) is any adverse event that commences after the start of administration of study drug.

An adverse events of special interest (AESI) is an adverse event of scientific or medical concern specific to the sponsor or the particular product or program, for which ongoing monitoring and rapid communication by the investigator to the sponsor may be appropriate.

The incidence of TEAEs (after dosing) will be summarized using the safety set. The MedDRA dictionary Version 21.0 (or higher) will be used to classify all AEs reported during the study by System Organ Class (SOC) and Preferred Term. A summary of TEAEs including the incidence of subjects who experienced TEAEs (number and percentage of subjects) and incidence of TEAEs (number of events) will be presented for each treatment group and overall, by severity and by relationship to study drug.

Serious TEAEs, AESIs (after dosing) and AEs leading to withdrawal will be summarized by SOC and Preferred Term for each treatment group and overall, and by relationship to study drug.

Subjects having multiple AEs within a category (e.g., overall, SOC and Preferred Term) will be counted once in that category. For severity tables, a subject's most severe event within a category will be counted. For relationship tables, a subject's event with greatest relationship to study drug within a category will be counted. In each table, SOC and Preferred Term will be presented in descending order of overall incidence rate (alphabetical order will be used in case of equal rates).

All adverse events will be listed.

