5.2 Laboratory Data

Clinical laboratory parameters (including blood chemistry, hematology, coagulation, urinalysis and other laboratory results) will be listed and abnormal parameters will be flagged as high (H) or low (L) according to reference ranges. Absolute (observed) values and changes from baseline (continuous variables) will be summarized for each parameter and scheduled time point by treatment group. The last lab value will be used for summary analysis if repeated measurements are made at any time point.

For summary statistics, a lab value with "<" will be replaced with a numeric value by removing the "<" sign. In the listings, the values will be displayed as originally reported by the laboratory.

Laboratory parameter values will be graded according to the Common Terminology Criteria for Adverse Events. Shift tables by treatment group will be produced for these laboratory parameters. These tables will summarize the number of subjects with each baseline grade relative to the normal ranges and changes to the worst highest grade assessed post-dose during the study.

The qualitative urinalysis data will be listed only.

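### An expected 8 of 12 placebo subjects were never randomised against the combination, and the SAP's safety tables and QTc models have no term or column for randomisation stage

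*SAP*

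**What the plan says.** **Allocation.** SAP 3.1 says that Treatment 1 was stopped once the first 20 randomised subjects had been dosed, and that "a total of 8 subjects have received treatment 1 before it was decided to terminate this arm". It continues: "Up to 24 further subjects will be included in the study, split in three cohorts of up to eight subjects". The later subjects are randomised among Treatments 2, 3 and 4 only, so that each of these arms reaches 12 over the whole study. The footnote to Table 6 (Protocol 6.1.2) confirms that nobody from Cohort 3 onwards receives the combination.

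**Safety tables.** SAP Section 5 sets the grouping: "Safety parameters will be summarized by treatment groups and, when relevant, overall". For AEs (5.1), the summary "will be presented for each treatment group and overall, by severity and by relationship to study drug". For laboratory data (5.2): "Shift tables by treatment group will be produced for these laboratory parameters". The ECG categories in 5.3 come under the same rule.

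**QTc models.** SAP 5.4.4 fits the change from baseline on a four-level treatment factor and centred baseline. SAP 5.4.5 adds plasma concentrations and a factor for nominal timepoint within the subject's own schedule. Neither has a term for stage, cohort or calendar time.

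**Limits on allocation in the first 20.** Protocol 3.3.4: "The sentinel group will consist of 4 subjects from treatment 1, and a minimum of 2 subjects each from treatments 2, 3 and 4". Protocol 3.3.7, for cohorts after Cohort 1: "A maximum of three subjects can be on the AQ + Malarone treatment arm within each cohort", with "a minimum of one subject from each of the continuing treatment arms". Protocol Table 3 (feature 1, limit II) requires at least two subjects per treatment in each dosing group after the sentinel group.

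**The concern.** The primary objective (SAP 2.1) compares the combination with placebo, and TEAE incidence is part of the primary endpoint (SAP 2.2). A placebo subject enrolled after the first 20 had no chance of being assigned the combination. Pooling those subjects with the earlier placebo subjects makes the combination-placebo comparison part randomised and part historical, and no planned table or model shows this to the reader.

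AEs are the more exposed outcome. They are reported by subjects or detected by the investigator, who also rates severity and causality (Protocol 8.2, 8.3). What subjects and staff may expect a subject to be receiving can change once the combination has been dropped. QTc is better protected, by blinded over-reading (Protocol 7.6.5) and by subtraction of each subject's own Day 1 baseline (SAP 5.4.2).

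Treatments 2 and 3 are little affected, because those arms and placebo all span both stages.

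**Working it through.** **1. The plan's own figure.** Inputs from SAP 3.1: 20 subjects while Treatment 1 was open, 8 of them on Treatment 1, and a target of 12 in each of Treatments 2 to 4. Further subjects needed = 3 × 12 − (20 − 8) = 24, which matches the plan. Total = 8 + 36 = 44.

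**2. Non-concurrent placebo.** Treatments 2 to 4 had equal shares of the allocation, so expected placebo in the first 20 = 12/3 = 4, and expected non-concurrent placebo = 12 − 4 = 8 of 12.

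For the range, infer that the first 20 were a sentinel group of 12 and a Cohort 2 of 8, with Treatment 1 at 4 + 4:
- Sentinel group: 8 places for Treatments 2 to 4, at least 2 each, so placebo 2 to 4.
- Cohort 2: 4 places, at least 1 each, so placebo 1 to 2.
- Concurrent placebo is 3 to 6, and non-concurrent placebo 6 to 9.
- Without the Cohort 2 minimum, placebo there is 0 to 4, concurrent placebo 2 to 8, and non-concurrent placebo 4 to 10.

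**3. Bias for arm means at one timepoint.** Let outcomes shift by d between stages, and let p be the number of placebo subjects in the first 20. The bias in Treatment 1 minus placebo has magnitude d(12 − p)/12:

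| p | Bias |
|---|---|
| 3 | 0.75d |
| 4 | 0.67d |
| 6 | 0.50d |

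Over the wider range of 4 to 10 non-concurrent subjects it is 0.33d to 0.83d. For Treatment 2 or 3 minus placebo it is 0 at equal splits and at most (6 − 3)/12 = 0.25d.

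Illustration with an assumed shift: 10 percentage points in AE incidence moves the combination-placebo difference by 6.7 points (5.0 to 7.5). For QTc, d must be a shift in the change from baseline.

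**4. Cost of adjusting for stage (SAP 5.4.4, one timepoint, variances in units of SD²).**
- Without stage: 1/8 + 1/12 = 0.2083.
- The stage effect is estimated within Treatments 2 to 4. At 4 + 8 per arm, its variance is 1/(3 × 4 × 8/12) = 1/8.
- With stage: 0.2083 + (8/12)² × 1/8 = 0.2639. Over the splits in step 2 that respect the Cohort 2 minimum, the range is 0.2417 to 0.2833.
- With t on 39 and 38 df, the 90% CI is 12.6% wider (7.8% to 16.7%). At an assumed SD of 10 ms, the half-width goes from 7.7 to 8.7 ms (8.3 to 9.0).
- Adjustment lowers mean squared error only if d exceeds SD × √(0.2639 − 0.2083)/0.667, which is 3.5 ms at SD 10 ms and 1.8 ms at SD 5 ms.

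**5. Precision of the concurrent column.** With no events, the upper 95% limit is 1 − 0.025^(1/n): 71% at n = 3, 60% at n = 4, 46% at n = 6, and 26% at n = 12.

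**6. The count of 8.** The sentinel group has 4 on Treatment 1 (Protocol 3.3.4) and Cohort 2 at most 3 (3.3.7), which gives at most 7. If Cohort 2 had 8 subjects with at least two per treatment (Table 3), each arm had exactly 2, which gives 6. Neither equals 8. At 7, non-concurrent placebo would be 5 to 9 of 12 and the bias 0.42d to 0.75d.

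**The case against.** The best defence is that nothing in the documents shows a difference between stages. The procedural changes that they record came after Cohort 1, inside the first 20: standing blood pressure, smaller cohorts, and the rules for extrapyramidal symptoms and rescue medication. Subjects and site staff remain blinded. The study is exploratory, safety is descriptive, and by-subject listings cover every randomised subject. The concurrent placebo group is also too small to settle anything. All of this stands, and it is why the point is about disclosure and sensitivity, not about replacing the analysis. It does not restore randomisation for the later placebo subjects. The listings are ordered by treatment and subject number, with no stage identifier specified.

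The second defence is precision. At SD 10 ms and a 3 ms shift in the change from baseline, mean squared error is 20.8 + 2.0² = 24.8 ms² pooled against 26.4 ms² with stage. Pooling can therefore be the better estimator, and this supports keeping the SAP's models as primary.

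A reader might infer that any QTc drift between stages biases the contrast. It does not: a shift in level present before and after dosing largely cancels in the change from baseline, and only a shift in the change itself matters. A reader might also carry the 0.67d factor to the 10 ms conclusion. That conclusion rests first on predictions from the 5.4.5 model at geometric mean Cmax, with concentration terms and random slopes. The SAP does not say whether the treatment coefficient enters them, so the factor cannot be transferred.

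**Conclusion.** The concern holds as a risk of bias and a gap in reporting. It is certain that Treatment 1 was randomised only in the first 20 subjects and that no planned table or model reflects this. Given 8 on Treatment 1, an expected 8 of 12 placebo subjects are non-concurrent. The range of 6 to 9 rests on an inferred 12 + 8 split and on applying the Cohort 2 minimum in Protocol 3.3.7, while the stated 8 does not fit the maximum in the same section. All ranges assume that every further place is dosed and that nobody is replaced (Protocol 5.2 allows replacement).

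The size is 0.67d (0.50d to 0.75d) for arm means at one timepoint, with d unknown. It matters most for AE incidence. The effect on the 5.4.5 predictions is not derived.

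The documents do not support the stronger inferences that the comparison is biased, or that the SAP orders both stages to be pooled. Pooling follows from the by-treatment specification; the protocol's sentence on pooled placebo (10.3) concerns the QTcF plot.

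**What to change.** Before database lock:

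1. **Tables.** In the shells for the AE, laboratory and categorical ECG tables, add a descriptive column for placebo from the first 20 subjects beside all placebo. Leave the placebo count by stage to be filled in after unblinding, because the codes stay in the pharmacy until then (SAP 3.4). State that most placebo subjects are expected to be non-concurrent with the combination.
2. **QTc.** Keep 5.4.4 and 5.4.5 as primary. Add one pre-specified sensitivity analysis of both with a two-level randomisation-stage factor, and report whether the combination-placebo estimate and the 10 ms conclusion change. Centre the factor, because SAP 5.4.8 uses the Day 1 time estimates directly. At 4 + 8 per arm, the one-timepoint variance of the placebo-reference time estimate is 0.083 SD² without stage, 0.085 with a mean-centred factor, and 0.139 with an uncentred factor that takes the first 20 as reference. A version with cohort is optional; it would also cover the changes made after Cohort 1.
3. **Count.** Reconcile the 8 in SAP 3.1 with Protocol 3.3.4, 3.3.7 and Table 3.

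The cost is SAP wording, one column and one sensitivity analysis, with no new data. The concurrent column rests on about 3 to 6 subjects and can only describe. The stage-adjusted by-timepoint CI is about 13% wider (8% to 17%) and assumes no stage-by-treatment interaction.

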5.1 Adverse Events

A Treatment Emergent Adverse Event (TEAE) is any adverse event that commences after the start of administration of study drug.

An adverse events of special interest (AESI) is an adverse event of scientific or medical concern specific to the sponsor or the particular product or program, for which ongoing monitoring and rapid communication by the investigator to the sponsor may be appropriate.

The incidence of TEAEs (after dosing) will be summarized using the safety set. The MedDRA dictionary Version 21.0 (or higher) will be used to classify all AEs reported during the study by System Organ Class (SOC) and Preferred Term. A summary of TEAEs including the incidence of subjects who experienced TEAEs (number and percentage of subjects) and incidence of TEAEs (number of events) will be presented for each treatment group and overall, by severity and by relationship to study drug.

Serious TEAEs, AESIs (after dosing) and AEs leading to withdrawal will be summarized by SOC and Preferred Term for each treatment group and overall, and by relationship to study drug.

Subjects having multiple AEs within a category (e.g., overall, SOC and Preferred Term) will be counted once in that category. For severity tables, a subject's most severe event within a category will be counted. For relationship tables, a subject's event with greatest relationship to study drug within a category will be counted. In each table, SOC and Preferred Term will be presented in descending order of overall incidence rate (alphabetical order will be used in case of equal rates).

All adverse events will be listed.

